Many factors have been shown to affect intraocular lens position: lens material, axial length of the eye, size of the capsulorrhesis, presence of posterior capsulotomy or asymmetric contraction of the capsular bag, viscoelastic removal, and final lens axis.⁵ Some surgeons have questioned whether a capsular tension ring (CTR) can reduce the amount of rotation. The capsular tension ring (CTR) is a thin, curved implant composed of polymethylmethacrylate. It stabilizes the capsular bag, equally distributing tension to centralize and stabilize the bag when zonules are weakened or missing.

The FDA has granted an Investigational Device Exemption (IDE# G190139) to approve the use of capsular tension rings in this study. This is considered a significant risk investigational device that is being used during routine cataract surgery as part of a clinical investigation. This extends the use of this device for eyes with normal, intact zonules and a stable lens capsule for the purposes of this study.

Previous studies have looked at rotational stability of toric IOLs with capsular tension rings and found that CTR improve stability. Rastogi *et al* randomized 50 eyes to Auromax toric IOL alone or toric IOL plus CTR.⁵ The eyes with a CTR rotated less than the eyes without the CTR, and the difference was statistically significant ($1.85 \pm 1.72^\circ$ in eyes with a CTR and $4.02 \pm 2.04^\circ$ in eyes without CTR, P-value = 0.003).

Several case reports and studies have looked at the effect of CTR in rotational stability in patients with axial myopia. Increasing axial length is associated with increased toric IOL rotation.⁶ Zhao *et al* studied 36 eyes with axial myopia, in which 16 were treated with CTR and 18 without.⁷ Acrysof SN6ATY IQ toric intraocular lenses were used. There was significantly less rotation with the use of CTR. A case report of two patients with high axial length demonstrated rotation when no CTR was inserted, but stability with use of the CTR.⁸ One patient had an AcrySof lens made by Alcon Laboratories, Inc. and one patient had Tecnis toric lens made by Johnson & Johnson Vision. An additional case report described an eye in which two CTR were required to prevent rotation in an AcrySof lens.⁹

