Measurements taken preoperatively on the IOL Master 700 will be used to determine the axial length of the study eye. If the axial length cannot be determined using the IOL Master 700, then the axial length measured by non-contact immersion A-scan will be used. For this study, the following selection protocol will be used (standard of care):

- Axial length > 28.0 mm: CTR model 14A
- Axial length 24.0-28.0 mm: CTR model 14C
- Axial length < 24.0 mm: CTR model 14

Labeling: The outer box of the capsular tension rings used in this study will be clearly labeled with the following statement: "CAUTION—Investigational Use. Limited by Federal (or United States) law to investigational use." This is in accordance with FDA-approved labeling procedures. In addition, the capsular tension ring selected for each eye will be packaged with the chosen intraocular lenses and labeled with the patient's name to prevent another patient receiving the device accidentally.

Randomization: Each eye undergoing cataract surgery will be randomized into a control or treatment group. If both eyes meet enrollment criteria, then each eye will be randomized independently. For patients able to enroll both eyes into the study, potential outcomes could be: a. one eye could be randomized into the control group and one eye could be randomized into the treatment group, b) both eyes could be randomized into the control group, or c) both eyes could be randomized into the treatment group.

- Control group: toric IOL only
- Treatment group: toric IOL plus capsular tension ring

Assignment of the eye to the control or treatment group will be revealed during the cataract surgery at the point of potential capsular tension ring insertion. The surgeon and clinical staff (ophthalmic technicians and nurses) will not know whether the eye is in the treatment/control group until after the cataract has been removed and it is time for potential capsular tension ring placement. The eye will have been previously assigned to the control or treatment group using a random number generator by clinical research personnel, who are not involved in patient care. The group assignment will be documented in an opaque, sealed envelope, which will be present in the operating room at the time of surgery. The envelope will be opened by operating room staff after lens removal, and the surgeon will be informed. If the capsular tension ring is to be implanted, the correct size will be selected and verified, then implanted.

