Reference 5 states eyes treated with a CTR rotated a mean 1.85°(1.72 SD) and eyes without a CTR rotated a mean 4.02°(2.04 SD). The minimum clinically significant difference of toric rotation away from the target axis the researchers wish to detect in this study is 1.85°. Using these parameters, a priori power for a repeated measures n analysis of variance (rANOVA) was assessed using G*Power Version 3.1.9.3. (12). The results indicate 50 subjects (eyes) will have a power of 0.957 at $\alpha = 0.05$ to detect this minimum clinically significant difference between the treatment groups.

Total sample and treatment group means, standard deviations, medians, interquartile ranges (IQR) and ranges will be calculated for interval variables. Frequency distributions will be produced for nominal and ordinal variables. Visual acuity, toric power, intended toric axis, and other variables will be included in the analysis.

The null hypothesis, H01, will be tested by a mixed effects repeated measures analysis of variance (rANOVA) using a general linear model, $y_{ij} = \mu + \alpha_i + \beta_j + \gamma_{ij} + \epsilon_{ij}$, where μ is the main treatment effect, α_i is time of repeated measure, and β_j represents the influence of individual j on his/her repeated observations.

[name], Senior Research Biostatistician Subject Matter Expert for Clinical Research Management under contracts OMNI 0004 3-82 and OMNI 0005 3-126, is the statistical consultant supporting this study. Statistical analysis will be performed with R Version 3.5.1. (13)

11.2 Sample Size:

50 eyes (approximately 25 eyes in each group) -- We are enrolling by number of eyes. If subjects have one eye that meets enrollment criteria, then that eye will be randomized into the treatment or control group. If both eyes meet enrollment criteria, then each eye will be randomized independently.

11.3 Total number of subjects requested (including records and specimens):

50

11.4 If you are recruiting by study arm, please identify the arms of the study and how many subjects will be enrolled in each arm

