Subjects will be a random sample of left or right eyes of male and female patients seen in one Air Force medical treatment facility. The patients are presumed to be randomly selected from the population of patients obtaining care at this Air Force medical treatment facilities.

The study is organized as a mixed effects, randomized design. Subject (eye) is a random effect, as the patients whose eyes are the subjects of this study are presumed to have been randomly elected to obtain this treatment from the population of patients obtaining similar care at these Air Force medical treatment facilities, and the subjects (eyes) are randomly assigned to treatment or control groups. Treatment is a fixed effect, as the effect of the intraocular lens and capsular tension ring cannot be generalized to other brands of toric intraocular lens or capsular tension rings.

Reference 5 states eyes treated with a CTR rotated a mean 1.85°(1.72 SD) and eyes without a CTR rotated a mean 4.02°(2.04 SD). The minimum clinically significant difference of toric rotation away from the target axis the researchers wish to detect in this study is 1.85°. Using these parameters, a priori power for a repeated measures n analysis of variance (rANOVA) was assessed using G*Power Version 3.1.9.3. (12). The results indicate 50 subjects (eyes) will have a power of 0.957 at $\alpha = 0.05$ to detect this minimum clinically significant difference between the treatment groups.

Total sample and treatment group means, standard deviations, medians, interquartile ranges (IQR) and ranges will be calculated for interval variables. Frequency distributions will be produced for nominal and ordinal variables.

The null hypothesis, H01, will be tested by a mixed effects repeated measures analysis of variance (rANOVA) using a general linear model, $y_{ij} = \mu + \alpha_i + \beta_j + \gamma_{ij} + \epsilon_{ij}$, where α is the main treatment effect, β is time of repeated measure, and γ_{ij} represents the influence of individual i on his/her repeated observations.

[name], Senior Research Biostatistician Subject Matter Expert for Clinical Research Management under contracts OMNI 0004 3-82 and OMNI 0005 3-126, is the statistical consultant supporting this study. Statistical analysis will be performed with R Version 3.5.1. (13)

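### The primary rotation model has no baseline covariate; pre-specifying one linear term for preoperative axial length would be a cheap improvement, with an uncertain and probably small gain

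*Combined protocol and SAP*

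**What the plan says.** The analysis of the primary outcome is described in 11.1 and again in 11.6: "The null hypothesis, H01, will be tested by a mixed effects repeated measures analysis of variance (rANOVA) using a general linear model". Each section then explains the terms. Apart from treatment and time, 11.1 has a term that "represents the influence of individual j on his/her repeated observations" and 11.6 one that "represents the influence of individual i on his/her repeated observations". The symbols are assigned differently in the two places, possibly through PDF conversion, and nothing here depends on that. Neither section defines a baseline covariate.

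A sentence in the descriptive-statistics paragraph of 11.1 promises that acuity, toric power, intended axis and unnamed further variables will go into the analysis. It gives them no role or functional form, does not mention axial length, and is missing from 11.6.

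Section 9.2 treats axial length as prognostic: "Many factors have been shown to affect intraocular lens position: lens material, axial length of the eye", followed by further factors, and then "Increasing axial length is associated with increased toric IOL rotation". It gives a direction but no size.

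Section 10.1 provides the measurement: "Measurements taken preoperatively on the IOL Master 700 will be used to determine the axial length of the study eye", with a fallback: "If the axial length cannot be determined using the IOL Master 700, then the axial length measured by non-contact immersion A-scan will be used". It adds that "the capsular tension ring selected for each eye will be packaged with the chosen intraocular lenses", and group assignment is revealed only during surgery, so the value should exist in both arms. Sections 10.1 and 11.4 describe allocation of each eye by random number generator and mention no stratification.

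**The concern.** The plan names a predictor of its own primary outcome, collects it before randomisation takes effect, and then leaves it out of the model. Among the factors listed in 9.2, axial length is the one that is a single continuous preoperative value with a stated direction. If it explains part of the variation in rotation, a linear term narrows the confidence interval and removes the linear part of any chance imbalance between two arms of about 25 eyes.

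Pre-specification is the second issue. The sentence in 11.1 leaves open which variables enter the model and in what form. Section 10.2 records visual acuity both before and after surgery, and 11.1 does not say which is meant; a postoperative value would not be a valid baseline covariate. Closing the list in advance has value whatever the correlation turns out to be.

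**Working it through.** **Inputs from the documents (11.1, 11.2, 10.1).** Difference to detect 1.85°; SDs 1.72° (ring) and 2.04° (no ring); about 25 eyes per arm; alpha 0.05; stated power 0.957; five postoperative visits.

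**Assumed.** Two-sided test; correlation r between axial length and rotation at one visit, 0 to 0.5; within-eye correlation ρ, 0.5 to 0.8. The documents give none of these.

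**1. The plan's own figure.** Pooled SD = √((1.72² + 2.04²)/2) = √3.56 = 1.887. SE of the difference = 1.887 × √(2/25) = 0.534. Noncentrality λ = (1.85/0.534)² = 12.02. Noncentral F with 1 and 48 df gives power 0.925 for one visit. For the mean of five visits the variance is 3.56 × (1 + 4ρ)/5:
- ρ = 0.8: variance 2.990, λ = 14.31, power 0.960
- ρ = 0.5: variance 2.136, λ = 20.03, power 0.992

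The stated 0.957 is met at ρ of about 0.82. A one-sided t test at one visit gives 0.962. The figure is therefore reachable, but only by supplying an input that the plan does not state.

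**2. Adding axial length with a common slope.** The variance of the difference becomes σ²(1 − r²)(2/25 + D²/S). Here D is the chance difference in mean axial length between arms (in SDs, variance 2/25) and S is the within-arm sum of squares (chi-square, 48 df). Power uses 1 and 47 df, averaged over D and S. For five visits the correlation with the eye mean is r/√0.84 (ρ = 0.8) or r/√0.60 (ρ = 0.5).

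| Setting | Unadjusted | r = 0 | r = 0.2 | r = 0.3 | r = 0.5 |
|---|---|---|---|---|---|
| One visit | 0.925 | 0.919 | 0.929 | 0.941 | 0.972 |
| Five visits, ρ = 0.8 | 0.960 | 0.956 | 0.964 | 0.972 | 0.992 |
| Five visits, ρ = 0.5 | 0.992 | 0.991 | 0.994 | 0.997 | >0.999 |

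Over five visits, r = 0.2 to 0.3 gains 0.2 to 0.5 points at ρ = 0.5 and 0.4 to 1.3 points at ρ = 0.8. At r = 0 the loss is about 0.4 points at most, or 0.6 with one visit. At r = 0.3 and one visit, the simulated mean 95% half-width falls from 1.07° to 1.03°.

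**3. Break-even.** (1 − r²)(1 + 1/46) = 1 gives r² = 1/47, so r = 0.146 for one visit. For five visits the same condition applies to the eye mean, so the per-visit r is slightly lower: 0.146 × √0.84 = 0.13, or 0.146 × √0.60 = 0.11.

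**4. Slope in control eyes only.** Simulated for five visits, ρ = 0.8, fitting a common slope. With correlations (control/treated) of 0.2/0, power goes from 0.960 to 0.958; with 0.3/0, from 0.960 to 0.961. The change is −0.2 to +0.1 points.

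**5. Chance imbalance.** The SD of the difference in mean axial length is √(2/25) = 0.283 SD, so P(|difference| > 0.3 SD) = 0.289. At r = 0.3, such an imbalance shifts the unadjusted estimate by 0.3 × 0.3 × 1.887 = 0.17°, which is 0.17/0.534 = 0.32 of its SE.

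**6. Fellow eyes.** With all 50 eyes as 25 pairs (assumed between-eye correlations 0.9 for axial length and 0.5 for residual rotation), five visits at ρ = 0.8 and analysis by eye as written, power is about 0.959 to 0.960 unadjusted. Adjusted, it is 0.958, 0.965 and 0.972 at r = 0, 0.2 and 0.3. The picture does not change.

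**The case against.** The strongest reply is that nothing is broken. Randomisation makes the unadjusted comparison valid, stated power is already 0.957, and a half-width change of about 0.04° is small against a 1.85° target. That stands, and it keeps this a suggestion for improvement.

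Second, 9.2 gives a direction and no size. A correlation of 0.1 fits the text equally well and would give a slight loss (0.921 against 0.925 with one visit). That also stands: a narrower interval is not assured.

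Third, a common slope is open to doubt. In the same section, the study in axial myopia reports less rotation with a ring, and two patients with high axial length had rotation without a ring and stability with one. If the ring acts that way, the slope is flatter in treated eyes and the gain is about zero (step 4).

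Fourth, 11.1 does mention further variables. But that sentence assigns no model role and omits axial length, so it does not answer the point; it leaves the covariate list open.

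A reader might infer that leaving axial length out biases the treatment effect, or that it is an uncontrolled confounder. The documents do not support this. Allocation is random, and the unadjusted interval already allows for chance imbalance of the size in step 5. Nor does choosing the ring model by axial length make adjustment improper, because axial length is measured before surgery.

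**Conclusion.** The point holds as a low-cost improvement. The primary model defines no baseline covariate, although the protocol names axial length as related to rotation and measures it for each study eye. Under the five-visit design the expected power change is about +0.2 to +1.3 points at r = 0.2 to 0.3 with a common slope, and about zero if only control eyes show the relation. At r = 0 the loss is at most about 0.4 points. These figures rest on assumed values of r and ρ, a two-sided test, 25 eyes per arm and the SDs quoted in 11.1. It would be wrong to conclude that the planned analysis is invalid or that adjustment is certain to help. The firmer benefit is a closed covariate list, which does not depend on r.

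**What to change.** In both 11.1 and 11.6, state: *The primary rotation model includes preoperative axial length (mm, continuous, one linear term with a slope common to both arms) as a fixed covariate. The unadjusted result is reported as a sensitivity analysis.*

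In 11.1, replace the sentence about acuity, toric power, intended axis and other variables with: *These variables are summarised descriptively and do not enter the primary model. No postoperative variable is used as a covariate. No other covariate enters the primary model unless it is named as a model covariate before any treatment-group data are analysed.* Without this replacement, the variables already listed there would remain arguably eligible.

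The cost is a few sentences, one degree of freedom, and a trivial loss of power if axial length is only weakly related to rotation. No new measurement is needed. Axial-length bands or an interaction with arm would use more degrees of freedom and are not proposed.

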11.5 Please provide a justification for your sample size

Subjects will be a random sample of left or right eyes of male and female patients seen in one Air Force medical treatment facility. The patients are presumed to be randomly selected from the population of patients obtaining care at this Air Force medical treatment facilities.

The study is organized as a mixed effects, randomized design. Subject (eye) is a random effect, as the patients whose eyes are the subjects of this study are presumed to have been randomly selected to obtain this treatment from a population of patients obtaining care at this Air Force medical treatment facility, and the subjects (eyes) are randomly assigned to treatment or control groups. Treatment is a fixed effect, as the effect of the intraocular lens and capsular tension ring cannot be generalized to other brands of toric intraocular lens or capsular tension rings.

Reference 5 states eyes treated with a CTR rotated a mean 1.85° (1.72 SD) and eyes without a CTR rotated a mean 4.02° (2.04 SD). The minimum clinically significant difference of toric rotation away from the target axis the researchers wish to detect in this study is 1.85° . Using these parameters, a priori power for a repeated measures n analysis of variance (rANOVA) was assessed using G*Power Version 3.1.9.3. (12). The results indicate 50 subjects (eyes) will have a power of 0.957 at $\alpha = 0.05$ to detect this minimum clinically significant difference between the treatment groups.

11.6 Data Analysis Plan: Complete description: Background, Objectives, Design, Step by Step how the project is going to be done, Data analysis plan:

The primary outcome and dependent variable will be the degree of toric rotation away from the target axis, and the time point of primary endpoint analysis will be when data for the last repeated measurement at 6 months has been obtained. The main treatment effect is a control group receiving a toric IOL only (Group 1) and a treatment group receiving a toric IOL plus capsular tension ring (Group 2). The statistical null hypotheses is as follows:

H01 — there is no difference in means of the degree of toric rotation away from the target axis between control and treatment groups

Subjects will be a random sample of left or right eyes of male and female patients seen in one Air Force medical treatment facility. The patients are presumed to be randomly selected from the population of patients obtaining care at this Air Force medical treatment facilities.

The study is organized as a mixed effects, randomized design. Subject (eye) is a random effect, as the patients whose eyes are the subjects of this study are presumed to have been randomly elected to obtain this treatment from the population of patients obtaining similar care at these Air Force medical treatment facilities, and the subjects (eyes) are randomly assigned to treatment or control groups. Treatment is a fixed effect, as the effect of the intraocular lens and capsular tension ring cannot be generalized to other brands of toric intraocular lens or capsular tension rings.

Reference 5 states eyes treated with a CTR rotated a mean 1.85°(1.72 SD) and eyes without a CTR rotated a mean 4.02°(2.04 SD). The minimum clinically significant difference of toric rotation away from the target axis the researchers wish to detect in this study is 1.85°. Using these parameters, a priori power for a repeated measures n analysis of variance (rANOVA) was assessed using G*Power Version 3.1.9.3. (12). The results indicate 50 subjects (eyes) will have a power of 0.957 at $\alpha = 0.05$ to detect this minimum clinically significant difference between the treatment groups.

Total sample and treatment group means, standard deviations, medians, interquartile ranges (IQR) and ranges will be calculated for interval variables. Frequency distributions will be produced for nominal and ordinal variables.

The null hypothesis, H01, will be tested by a mixed effects repeated measures analysis of variance (rANOVA) using a general linear model, $y_{ij} = \mu + \alpha_i + \beta_j + \gamma_{ij} + \epsilon_{ij}$, where α is the main treatment effect, β is time of repeated measure, and γ_{ij} represents the influence of individual i on his/her repeated observations.

[name], Senior Research Biostatistician Subject Matter Expert for Clinical Research Management under contracts OMNI 0004 3-82 and OMNI 0005 3-126, is the statistical consultant supporting this study. Statistical analysis will be performed with R Version 3.5.1. (13)

12.0 Participant Information

12.1 Subject Population:

Active duty and DoD beneficiaries aged 30 years or older undergoing cataract surgery. Patients who are pregnant or lactating will be excluded because the risks of surgery and post-operative medication to the unborn fetus are unknown. Patients under 30 years of age will not be included because they are likely to have congenital, pediatric, or juvenile-onset cataracts, which is outside the scope of this study. Corneal astigmatism ≥ 1.0 D and a surgical plan that includes a toric intraocular lens for astigmatism correction.

12.2 Age Range:

Check all the boxes that apply. If the age range of potential subjects (specimens, records) does not match the range(s) selected, please specify in the text box.

- 0-17
- 18-24
- 25-34
- 35-44

45-54
 55-64
 65-74
 75+

12.3 Gender:

Male
 Female
 Other

12.4 Special categories, check all that apply

Minors /Children
 Students
 Employees - Civilian
 Employees - Contractor
 Resident/trainee
 Cadets /Midshipmen
 Active Duty Military Personnel
 Wounded Warriors
 Economically Disadvantaged Persons
 Educationally Disadvantaged Persons
 Physically Challenged (Physical challenges include visual and/or auditory impairment)
 Persons with Impaired Decisional Capacity
 Prisoners
 Pregnant Women, Fetuses, and Neonates
 Non-English Speakers
 International Research involving Foreign Nationals - Headquarters Review is necessary

You must also consider the requirements of DoDI 3216.02, Enclosure 3, paragraph 7.e.

12.5 Inclusion Criteria:

Order Number	Criteria
1	
 • Active duty and DoD beneficiaries aged 30 years or older undergoing cataract surgery • Corneal astigmatism = 1.0 D and a surgical plan that includes a toric intraocular lens for astigmatism correction. 
 ◦ The lenses used will be the Tecnis Toric II IOL and the Eyhance Toric II IOL (Johnson & Johnson Vision). The lenses will be used on label. • No observed zonular or capsular problems prior to, or at the time of, capsular tension ring insertion

12.6 Exclusion Criteria:

Order Number	Criteria
	
 • Patients who are pregnant or lactating

1

- Patients undergoing cataract surgery who do not have corneal astigmatism =1.0 D.
- Any observed zonular or capsular problems prior to, or at the time of, capsular tension ring insertion.
- Pre-existing ocular conditions, including:
 - Pseudoexfoliation syndrome in one or both eyes
 - Prior incisional ocular surgery
 - Lens subluxation
 - Poor dilation or inability to position at the slit lamp (making postoperative outcome measurements difficult or impossible)
 - Plans for extensive travel or to move away during the postoperative evaluation period
 - Other conditions that would influence the capsule or lens positioning
- Surgical plan that includes other procedures at the time of initial cataract surgery, such as Limbal Relaxing Incisions (LRIs), Micro-Incisional Glaucoma Surgery (MIGS), etc.
- Legally Authorized Representatives will not be utilized in this study

